6.3.3 Handling of intercurrent events and missing data

Subjects for whom the endpoint is missing because of missing diary data or missing pollen exposure (see Section 9.1), multiple imputation will be from own treatment group in case of no intercurrent event has occurred, otherwise below imputation rules will be applied. Data is assumed to be MAR.

Subjects with imputed endpoint, will be included in the statistical model with their original treatment group, age group, cohort, and pollen station.

6.3.3.1 Handling of intercurrent events and missing data for the trial product estimand

For the trial product estimand, diary data occurring after discontinuation of trial treatment will be excluded from the derivation of the primary endpoint (see section 9.2.2.3). Subjects for whom the primary endpoint is missing (because of either missing diary data or the exclusion of diary data due to discontinuation of trial treatment) will be included in the analysis through multiple imputation under the hypothetical situation where subjects continued to take trial treatment as planned.

Multiple imputation for subjects missing the primary endpoint will be conducted as follows:

- For subjects that discontinue trial treatment due to lack of efficacy, multiple imputation of the missing endpoint will be from the placebo group. This assumes that had the subject continued to take trial treatment, they would have experienced similar efficacy to subjects in the placebo arm. Data is assumed to be MNAR.
- For subjects that discontinue trial treatment due to treatment-related AEs, multiple imputation of the missing endpoint will be from their own treatment group. This assumes that the level of efficacy that would have been experienced by the subject if they had

continued to take trial treatment is unrelated to the occurrence of the AE and, if they had continued to take trial treatment, they would have experienced similar efficacy to subjects in their own treatment group. Data is assumed to be MAR.

- For subjects that discontinue trial treatment due to any other non-treatment related reason, multiple imputation of the missing endpoint will be from their own treatment group. This assumes that the level of efficacy that would have been experienced by the subject had they continued to take trial treatment is not related to their discontinuation of trial treatment. Data is assumed to be MAR.

6.3.3.2 Handling of intercurrent events and missing data for the treatment policy estimand

For subjects discontinuing trial treatment, all diary data (including data collected after discontinuation of trial treatment) will be included in the derivation of the primary endpoint (see section 9.2.1.4). Subjects for whom the primary endpoint is missing will be included in the analysis through multiple imputation as follows:

- For subjects discontinuing trial treatment due to treatment-related AEs or lack of efficacy, multiple imputation of the missing endpoint will be from the placebo group. This assumes that missing data following treatment-related discontinuation of trial treatment is MNAR and that subjects no longer taking active treatment for these reasons would have shown similar efficacy to subjects receiving placebo.
- For subjects discontinuing trial treatment due to non-treatment related reasons, multiple imputation of the missing endpoint will be from their own treatment group. This assumes that the missing data are MAR.

6.3.3.3 Sensitivity analyses

The sensitivity estimator for both estimands will be the absolute treatment difference.

The sensitivity estimator for both estimands will be based on an identical method of statistical analysis although the actual data used in each analysis may vary according to the different strategies taken for the handling of intercurrent events and missing data. Further details of the different strategies for each estimand are provided in sections 6.3.3.4 and 6.3.3.5.

6.3.3.4 Sensitivity analysis for the product trial estimand

The sensitivity estimator for the trial product estimand will use the multiple imputation policy described for the main estimator (see section 6.3.3.1) except that:

- For subjects that discontinue trial treatment due to treatment-related AEs, multiple imputation of the missing endpoint will be from the placebo group. This assumes subjects reporting treatment-related AEs would have been experienced a level of efficacy similar to subjects in the placebo group if they had continued to take trial treatment. Data is assumed to be MNAR.

An additional sensitivity estimator will be performed to investigate the MAR assumption for the imputation in the sensitivity estimator above. The analysis will be performed as follows: a penalty (a number) is added to all imputed values in the active treatment group, and the analysis is repeated on the FAS population for the trial product estimand. The penalty is gradually increased until the point, the tipping point, where the null hypothesis is no longer

rejected. If the tipping point is considered a clinical plausible difference, the tipping-point analysis does not support the sensitivity estimator.

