6.3 Primary endpoint analysis

6.3.1 Definition of endpoint

The primary endpoint is the average TCS during the BPS. The average TCS during the BPS is the average of the daily sum of the DSS and DMS during the BPS.

6.3.2 Main estimator, sensitivity estimator(s) and statistical analysis for the trial product and treatment policy estimands

The main estimator for both estimands will be the absolute treatment difference.

The main estimator for both estimands will be based on an identical method of statistical analysis (specified below), although the actual data used in each analysis may vary according to the different strategies taken for the handling of intercurrent events and missing data. Further details of the different strategies for each estimand are provided in sections 6.3.3.1, 6.3.3.2, and 6.4.1.

Analyses will be based on all randomised subjects. Subjects for whom the efficacy endpoint is missing will be included in the analysis through multiple imputation, where missing data will be

imputed from the same age group according to the approaches specified in sections 6.3.3.1, 6.3.3.2, and 6.4.1. Imputation will use the method of unrestricted random sampling with replacement (seed=7127) and 1000 multiply imputed datasets will be created. For each dataset, the efficacy endpoint will be square root transformed in order for the residuals to fulfil the underlying assumption of following the so-called statistical normal distribution and analysed using a linear mixed effects model assuming unequal variances in the 2 treatment groups. The model will include treatment, cohort (1, 2), and age group (5-11 years, 12-17 years) as fixed effects and pollen station within cohort as a random effect, with different residual errors specified for each treatment group. The model will be estimated using REML, and the denominator degrees of freedom will be calculated using the Kenward and Roger's approximation (Kenward and Roger 1997).

Rubin's rule is used to combine the 1000 analysis results across the multiple imputed datasets. The p-value for the absolute difference is reported as the test result.

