6.5 Summary of primary and key secondary endpoints analyses and figures

An overview of analyses for the primary and key secondary endpoints are presented in Table 6.

Table 6: Overview of analyses for the primary and key secondary endpoints

Endpoint	Description	Population	Model	Analysis name	Multiple imputation		
					Reason for IMP discontinuation' and not 'IE handling	Imputation group	Assumption
Average TCS during BPS	Trial product estimand	FAS	LME with MI	Main estimator	
 • Lack of efficacy • Treatment-related AEs • Other non treatment-related reasons 	
 • Placebo • Own treatment group • Own treatment group 	
 • MNAR • MAR • MAR
				Sensitivity estimator	
 • Lack of efficacy • Treatment-related AEs • Other non treatment-related reasons 	
 • Placebo • Placebo • Own treatment group 	
 • MNAR • MNAR • MAR
				Sensitivity (tipping point)	
 • Lack of efficacy • Treatment-related AEs • Other non treatment-related reasons 	
 • Placebo • Placebo • Own treatment group (penalty on active group) 	
 • MNAR • MNAR • MAR
				Supplementary	
 • Lack of efficacy • Treatment-related AEs • Other non treatment-related reasons 	
 • Placebo • Own treatment group • Own treatment group 	
 • MNAR • MAR • MAR
	Treatment policy estimand		LME with MI	Main estimator	
 • Lack of efficacy • Treatment-related AEs • Other non treatment-related reasons 	
 • Placebo • Placebo • Own treatment group 	
 • MNAR • MNAR • MAR
				Sensitivity estimator	
 • All reasons 	
 • Placebo 	
 • MNAR

	Observed case		LME	Supportive	-	-	-	
Average TCS during TPS	Trial product estimand	FAS	LME with MI	Main estimator	
 • Lack of efficacy • Treatment-related AEs • Other non treatment-related reasons 	
 • Placebo • Own treatment group • Own treatment group 	
 • MNAR • MAR • MAR 	

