6.11 Changes and/or deviations to protocol-planned analyses

In addition to the analyses specified in the CTP a supplementary analysis for the primary endpoint has been added where subjects with potential data issues will be excluded from the main analysis.

The secondary endpoints (average TCS during the AHPS and OPS, average DSS during the AHPS and OPS, average DMS during the AHPS and OPS, and average TCS (EAACI scoring) during BPS and TPS) will be analysed by using the hypothetical estimand and main estimator only.

Local administration site reactions are specified as 'treatment-related local administration site TEAEs.

The reasons for IMP discontinuation will be visualised by a band plot, instead of a Kaplan-Meier plot as the band plot also shows the different reasons for discontinuation.

Physical examination will not be summarized by visit as stated in the CTP, instead a shift table will be made from baseline to end of treatment. 5-, 25-, 75-, and 95 percentiles will not be presented for tabulation of data by visit as stated in the CTP.

The exploratory assessment of the levels of serum antibodies/serum components/serum markers to relevant allergens will not be performed nor reported in a separate document as stated in CTP.

Due to the amount of missing pollen data, it was deemed necessary to perform a visual inspection of all species by pollen station instead of the pollen plots (pollen grains/m³ versus time) as the approach chosen is more precise.

7 Sample size determination

Sample size calculations are based on the primary endpoint, the average TCS during the BPS, which will be square root transformed prior to analysis in order to better approximate the normal distribution. Based on previous ALK SLIT-tablet studies in both adult and paediatric populations, it is assumed that the mean of the square root transformed average TCS during the BPS in the placebo group is 2.5 with corresponding common standard deviation of 1.4 in both placebo and active groups.

Analyses for the primary and secondary estimands will include all randomised subjects and use different multiple imputation strategies to account for missing data. For the purposes of sample size estimation, it is assumed that 5% of observations in the active arm are imputed from the placebo arm. A true relative treatment effect of 25% is assumed, which corresponds to an effective relative treatment effect of 23.75% after placebo imputation.

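### The tipping-point analysis is meant to test MAR, but SAP 6.3.3.4 also penalises active-arm values already imputed from placebo under MNAR, while Table 6 does not

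*SAP*

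**What the plan says.** SAP 6.3.3.4 defines two sensitivity analyses for the trial product estimand. The first changes the main estimator in one respect: treatment-related adverse-event discontinuers are imputed from placebo under MNAR. Lack-of-efficacy discontinuers were already imputed that way (SAP 6.3.3.1). Other discontinuers are imputed from their own group under MAR. So are subjects whose endpoint is missing without an intercurrent event: SAP 6.3.3 says "multiple imputation will be from own treatment group in case of no intercurrent event has occurred".

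The second is the tipping-point analysis. Its purpose is that it is "performed to investigate the MAR assumption for the imputation in the sensitivity estimator above". Its rule is that "a penalty (a number) is added to all imputed values in the active treatment group", with the penalty raised until the null hypothesis is no longer rejected. The result carries a consequence: "If the tipping point is considered a clinical plausible difference, the tipping-point analysis does not support the sensitivity estimator".

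SAP 6.3.3 also fixes which group an imputed subject belongs to: "Subjects with imputed endpoint, will be included in the statistical model with their original treatment group".

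The tipping-point row of SAP Table 6 (section 6.5) has three lines. Lack of efficacy and treatment-related adverse events are listed as placebo, MNAR, with no penalty. The third line, other reasons under MAR, reads "Own treatment group (penalty on active group").

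**The concern.** The purpose, the text rule and the table do not agree. Only own-group imputations rest on MAR, so a test of MAR should shift those and leave the rest alone. Because imputed subjects keep their randomised group, the phrase covering every imputed value in the active arm also takes in subjects whose values were drawn from placebo. Penalising them assumes they would have done worse than placebo, which the SAP neither states nor justifies and which is not a departure from MAR.

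A programmer working from 6.3.3.4 and one working from Table 6 would penalise different records and report different tipping points. SAP 6.11 does not mention this analysis, and protocol 15.12.2 only leaves further sensitivity estimators to the SAP. Since the SAP draws a conclusion from whether the tipping point is clinically plausible, the choice of records can affect what is concluded about robustness.

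**Working it through.** **Inputs.** From SAP section 7: placebo mean 2.5 and SD 1.4 on the square-root scale, 500 subjects per arm, a 25% relative effect, and 10% of subjects without diary data in the birch season. The same section says "it is assumed that 5% of observations in the active arm are imputed from the placebo arm". From SAP 6.1: two-sided 5% level. The SAP gives no split by imputation source for this estimator, so the split is an assumption and is varied below.

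**Reproducing the plan's figure.** The SAP states no tipping-point value, but the planning inputs can be checked against the power in SAP Table 7.

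- FAS: difference = 2.5 − √(6.25 × (1 − 0.2375)) = 0.317; SE = 1.4 × √(2/500) = 0.0885; z = 3.58; power = Φ(3.58 − 1.96) = 94.7% (stated 95.0%).
- Observed case: difference = 2.5 − √(6.25 × 0.75) = 0.335; SE = 1.4 × √(2/450) = 0.0933; z = 3.59; power = 94.8% (stated 94.7%).

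The inputs are therefore read as the SAP intended.

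**Tipping-point calculation.** Square-root TCS is taken as N(2.5, 1.4) on placebo and N(2.5 × √(1 − effect), 1.4) on active, floored at 0. The active arm is 90% observed, with the other 10% divided between own-group and placebo imputation. A penalty d turns an imputed value u on the square-root scale into √(u² + d): it is added to TCS before the transformation, following the order of steps in SAP 6.3.2 ("For each dataset, the efficacy endpoint will be square root transformed in order for the residuals to fulfil the underlying assumption"). Then

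z(d) = (placebo mean − active mixture mean) / √(placebo variance/500 + active mixture variance/500),

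and d is solved for z(d) = 1.96. Covariates and between-imputation variance are ignored.

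Tipping penalty in TCS points, text rule vs Table 6 rule:

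| Relative effect | 5% placebo, 5% own | 2.5% placebo, 7.5% own |
|---|---|---|
| 25% | 7.1 vs 17.0 | 7.4 vs 10.6 |
| 20% | 3.2 vs 7.5 | 3.5 vs 4.9 |
| 18% | 1.9 vs 4.4 | 2.2 vs 3.0 |
| 16% | 0.8 vs 1.75 | 1.0 vs 1.4 |

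With no placebo imputation the two rules coincide (7.8 at 25%). For the 5%/5% split, z before any penalty is 3.6 at a 25% effect and 2.2 at 16%, so both start from a significant result.

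**Why the gap arises.** If the penalty is instead added on the square-root scale and the SE is held fixed, the ratio of the two tipping points is (placebo share + own share) / own share. That is (5 + 5)/5 = 2 for an even split, and 1.25 for 2% placebo with 8% own. A fixed-SE version gives 1.19 vs 2.39 on that scale at 25% and 5%/5%, and 6.1 vs 14.9 when the penalty is added to TCS.

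**Finite-sample check at a 25% effect.** This used 120 simulated trials, sampling with replacement, 60 imputations, Rubin's rule and 10% of placebo also imputed. Among significant trials the median tipping penalty was 8.1 vs 19.2 for 5%/5% (interquartile ranges 4.4–11.4 and 10.2–27.8), and 7.0 vs 9.8 for 2.5% placebo with 7.5% own. The direction holds; the values vary widely between trials.

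**Where the reading could matter.** One natural benchmark is the penalty that brings own-group imputations down to placebo level. At a 16% effect that is about 0.16 × 6.25 = 1.0 TCS point. With the 5%/5% split the text tips before it (0.8) and Table 6 after it (1.75).

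**The case against.** The strongest reply is that the text errs in one direction only. It penalises everything Table 6 penalises and more, so it tips no later than Table 6. If the text version supports the sensitivity estimator, so does the table version; the only possible error is a false finding of non-support, which goes against the product. That is correct, and it is why the point is minor.

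The case where the readings divide is also narrow. With the 5%/5% split and the placebo-level benchmark, they separate only at effects of about 15.5% to 16%. At 16.5% both tip past the benchmark (1.06 and 2.35 against 1.04); at 15% both tip before it (0.31 and 0.68 against 0.95). In that window the estimate after placebo imputation is already about 0.9, below the EMA criterion of 1 in SAP section 7. On the square-root scale both tip beyond placebo level at 16% (0.22 and 0.45 against about 0.2), and the window moves slightly lower. The SAP gives no plausibility threshold, so any benchmark is the reader's choice. All of this stands, and the 16% case should be taken only as an illustration that divergence is possible.

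It can also be said that Table 6 is an overview and that its parenthesis may mean only that the placebo arm is not penalised. That is possible, but the note stands on one line of three, and that placement is the one that fits the stated purpose. Penalising every imputed active value would be a legitimate stress test under that name. It is not a test of MAR.

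**Conclusion.** The concern holds. As written, the rule in SAP 6.3.3.4 does not isolate the assumption it is said to investigate, and Table 6 points to a different set of records. With the assumed splits, the text's tipping penalty is between about 40% and 75% of the Table 6 value (7.1/17.0 = 0.42; 1.0/1.4 = 0.71). The gap grows with the share imputed from placebo and vanishes when that share is zero.

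The consequence is limited. This is one sensitivity analysis of the primary endpoint, outside the testing hierarchy. The primary test, estimate and confidence interval do not change. At the planned 25% effect both readings give penalties of about 7 TCS points or more, so the conclusion would probably be the same. The correction should be made, but it does not threaten the trial's main result. The figures rest on the planning values, an assumed imputation split, a penalty added before the square root, and a large-sample approximation.

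**What to change.** In SAP 6.3.3.4, state that the penalty applies only to active-arm values imputed from the active group under MAR, including endpoints missing without an intercurrent event, and that values imputed from placebo are not penalised. Put the same scope in the tipping-point row of Table 6, which at present does not list the no-intercurrent-event case. It would help to confirm in the same sentence that the penalty is added to average TCS before the square-root transformation. If the broader penalty is also wanted, report it separately as a stress test on all imputed active values.

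The cost is one sentence, one table note and a record filter in the tipping-point programme. If the SAP can no longer be changed, the scope used should be recorded in the trial report as a clarification, with both results shown.

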6.3.3.5 Sensitivity analysis for the treatment policy estimand

The sensitivity estimator for the treatment policy estimand will use multiple imputation from the placebo group for all subjects that discontinue trial treatment regardless of the reason for discontinuation. Data is assumed to be MNAR.

6.3.4 Supportive analyses

For the primary and key secondary efficacy endpoints, an observed case analysis based on all subjects with at least one diary entry in the relevant pollen season will be performed as a supportive analysis. This analysis will allow comparison of results both to previous trials where the primary efficacy analyses were based on observed cases and also to acknowledged criteria for clinical success, which were established based on observed case analyses.

6.3.5 Supplementary analyses

A supplementary analysis for the primary endpoint will be performed using the main estimator of the trial product estimand (see section 6.3.2). Subjects with potential data issues listed in (VV-CLIN-005043) will be excluded from the analysis.

6.4 Key secondary endpoint analyses

6.4.1 Estimators for estimands defined for key secondary efficacy objectives

The key secondary endpoints, average TCS during the TPS, average DSS during the BPS and TPS, and average DMS during the BPS and TPS will be analysed identically to the primary endpoint using the definitions of the trial product estimand and treatment policy estimand (see sections 3.1.1.1 and 3.1.1.2 respectively) and the main, sensitivity, and supportive estimators described in section 6.3.3, except for the tipping point analysis.

6.5 Summary of primary and key secondary endpoints analyses and figures

An overview of analyses for the primary and key secondary endpoints are presented in Table 6.

Table 6: Overview of analyses for the primary and key secondary endpoints

Endpoint	Description	Population	Model	Analysis name	Multiple imputation		
					Reason for IMP discontinuation' and not 'IE handling	Imputation group	Assumption
Average TCS during BPS	Trial product estimand	FAS	LME with MI	Main estimator	
 • Lack of efficacy • Treatment-related AEs • Other non treatment-related reasons 	
 • Placebo • Own treatment group • Own treatment group 	
 • MNAR • MAR • MAR
				Sensitivity estimator	
 • Lack of efficacy • Treatment-related AEs • Other non treatment-related reasons 	
 • Placebo • Placebo • Own treatment group 	
 • MNAR • MNAR • MAR
				Sensitivity (tipping point)	
 • Lack of efficacy • Treatment-related AEs • Other non treatment-related reasons 	
 • Placebo • Placebo • Own treatment group (penalty on active group) 	
 • MNAR • MNAR • MAR
				Supplementary	
 • Lack of efficacy • Treatment-related AEs • Other non treatment-related reasons 	
 • Placebo • Own treatment group • Own treatment group 	
 • MNAR • MAR • MAR
	Treatment policy estimand		LME with MI	Main estimator	
 • Lack of efficacy • Treatment-related AEs • Other non treatment-related reasons 	
 • Placebo • Placebo • Own treatment group 	
 • MNAR • MNAR • MAR
				Sensitivity estimator	
 • All reasons 	
 • Placebo 	
 • MNAR

	Observed case		LME	Supportive	-	-	-	
Average TCS during TPS	Trial product estimand	FAS	LME with MI	Main estimator	
 • Lack of efficacy • Treatment-related AEs • Other non treatment-related reasons 	
 • Placebo • Own treatment group • Own treatment group 	
 • MNAR • MAR • MAR 	
				Sensitivity estimator	
 • Lack of efficacy • Treatment-related AEs • Other non treatment-related reasons 	
 • Placebo • Placebo • Own treatment group 	
 • MNAR • MNAR • MAR 	
	Treatment policy estimand		LME with MI	Main estimator	
 • Lack of efficacy • Treatment-related AEs • Other non treatment-related reasons 	
 • Placebo • Placebo • Own treatment group 	
 • MNAR • MNAR • MAR 	
				Sensitivity estimator	
 • All reasons 	
 • Placebo 	
 • MNAR 	
	Observed case		LME	Supportive	-	-	-	
	Average DSS during BPS	FAS	LME with MI	Main estimator	
 • Lack of efficacy • Treatment-related AEs • Other non treatment-related reason 	
 • Placebo • Own treatment group • Own treatment group 	
 • MNAR • MAR • MAR 	
				Sensitivity estimator	
 • Lack of efficacy • Treatment-related AEs • Other non treatment-related reasons 	
 • Placebo • Placebo • Own treatment group 	
 • MNAR • MNAR • MAR 	
	Treatment policy estimand		LME with MI	Main estimator	
 • Lack of efficacy • Treatment-related AEs • Other non treatment-related reasons 	
 • Placebo • Placebo • Own treatment group 	
 • MNAR • MNAR • MAR 	
				Sensitivity estimator	
 • All reasons 	
 • Placebo 	
 • MNAR 	

	Observed case		LME	Supportive	-	-	-	
Average DSS during TPS	Trial product estimand	FAS	LME with MI	Main estimator	
 • Lack of efficacy • Treatment-related AEs • Other non treatment-related reasons 	
 • Placebo • Own treatment group • Own treatment group 	
 • MNAR • MAR • MAR 	
				Sensitivity estimator	
 • Lack of efficacy • Treatment-related AEs • Other non treatment-related reasons 	
 • Placebo • Placebo • Own treatment group 	
 • MNAR • MNAR • MAR 	
	Treatment policy estimand		LME with MI	Primary	
 • Lack of efficacy • Treatment-related AEs • Other non treatment-related reasons 	
 • Placebo • Placebo • Own treatment group 	
 • MNAR • MNAR • MAR 	
				Sensitivity estimator	
 • All reasons 	
 • Placebo 	
 • MNAR 	
	Observed case		LME	Supportive	-	-	-	
Average DMS during BPS	Trial product estimand	FAS	LME with MI	Main Estimator	
 • Lack of efficacy • Treatment-related AEs • Other non treatment-related reasons 	
 • Placebo • Own treatment group • Own treatment group 	
 • MNAR • MAR • MAR 	
				Sensitivity estimator	
 • Lack of efficacy • Treatment-related AEs • Other non treatment-related reasons 	
 • Placebo • Placebo • Own treatment group 	
 • MNAR • MNAR • MAR 	
	Treatment policy estimand		LME with MI	Main estimator	
 • Lack of efficacy • Treatment-related AEs • Other non treatment-related reasons 	
 • Placebo • Placebo • Own treatment group 	
 • MNAR • MNAR • MAR 	
				Sensitivity estimator	
 • All reasons 	
 • Placebo 	
 • MNAR 	

	Observed case		LME	Supportive	-	-	-	
Average DMS during TPS	Trial product estimand	FAS	LME with MI	Main estimator	
 • Lack of efficacy • Treatment-related AEs • Other non treatment-related reasons 	
 • Placebo • Own treatment group • Own treatment group 	
 • MNAR • MAR • MAR 	
				Sensitivity estimator	
 • Lack of efficacy • Treatment-related AEs • Other non treatment-related reasons 	
 • Placebo • Placebo • Own treatment group 	
 • MNAR • MNAR • MAR 	
	Treatment policy estimand		LME with MI	Main estimator	
 • Lack of efficacy • Treatment-related AEs • Other non treatment-related reasons 	
 • Placebo • Placebo • Own treatment group 	
 • MNAR • MNAR • MAR 	
				Sensitivity estimator	• All reasons	• Placebo	• MNAR	
	Observed case		LME	Supportive	-	-	-	

